6.1.3.1 Model checking procedures

Not applicable

6.1.3.2 Graphical presentation of results

Results will be displayed tabular and graphically, where the conversion rate (80% CI) for each treatment will be displayed in dot plots and a forest plot.

6.1.3.3 Sensitivity analysis

6.1.3.4 Supplementary analysis

Commercially Confidential Information

6.2 Secondary objectives

There are no secondary PD objectives.

6.3 Exploratory objectives

Commercially Confidential Information

6.3.1 Variables

6.3.2 Descriptive analyses Commercially Confidential Information

6.3.3 Statistical model, assumptions and hypotheses Commercially Confidential Information

6.3.4 Graphical presentation of results

Commercially Confidential Information

7 Statistical methods for safety and tolerability data

The secondary safety objectives are to evaluate the safety and tolerability of HSY244 in participants with AF.

7.1 Variables

Adverse events, vital signs (blood pressure, pulse rate, body temperature), laboratory measurements, as well as participant demographics, baseline characteristics, and treatment information.

The values for the ECG intervals (PR interval, QRS duration, heart rate, RR, QT, QTcF). For these ECG parameters described, the central reader values will be used for analysis. These parameters will be derived from the single time point ECG data.

Heart rate will be analyzed using both the safety analysis dataset and the PD analysis dataset.

7.2 Descriptive analyses

Participant demographics and other baseline characteristics

Demographic and other baseline data including disease characteristics will be listed and summarized descriptively by treatment group and cohort for the safety analysis set.

Categorical data will be presented as frequencies and percentages. For continuous data, mean, standard deviation, median, minimum, and maximum will be presented.

Relevant medical histories and current medical conditions at baseline will be summarized by system organ class and preferred term by treatment group and cohort. For AF disease history, if the start month is missing, then the start month will be imputed as 'JAN'. Similarly, if the start day is missing, the start day will be imputed as '01'.

Treatment

Data for study drug administration (rescue medication), concomitant medications and significant non-drug therapies prior to and after the start of the study treatment will be listed and summarized according to the Anatomical Therapeutic Chemical (ATC) classification system by treatment group and cohort.

Vital signs

All vital signs data will be listed by treatment group, cohort, participant, and visit/time and if ranges are available, abnormalities (and relevant orthostatic changes) will be flagged. Summary statistics will be provided by treatment, cohort and visit/time.

ECG evaluations

- 1. PR, QRS, QT, QTcF, and RR intervals will be obtained from single time point ECGs for each participant during the study. ECG data will be read and interpreted locally for initial safety readouts. The single time point ECGs will be read centrally for the parameters above and these will be reported in the CSR.
- 2. Categorical Analysis of QT/QTcF interval data based on the number of participants meeting or exceeding predefined limits in terms of absolute QT intervals or changes from baseline will be presented. In addition, a listing of these participants will be produced (by treatment group).

QT/QTcF and QRS duration will be examined separately between individuals with and without a complete bundle branch block.

All ECG data will be listed by treatment group, cohort, participant, and visit/time, and abnormalities will be flagged.

Summary statistics will be provided by treatment, cohort and visit/time.

Commercially Confidential Information

These descriptive statistics will be generated for all observations, observations where participants are in AF and observations where participants are in sinus rhythm.

The MMRM and concentration-effect analyses described in Section 6.3.3 may also be used for the ECG parameters described above.

Clinical laboratory evaluations

All laboratory data will be listed by treatment, participant, and visit/time and if normal ranges are available abnormalities will be flagged. A separate listing is provided presenting all parameters in a participant with any abnormal values. Summary statistics will be provided by treatment, visit/time and cohort.

Adverse events

All information obtained on adverse events will be displayed by treatment, participant and cohort.

The number and percentage of participants with adverse events will be tabulated by body system and preferred term with a breakdown by treatment. An adverse event starting in one period and continuing into the next period is counted only in the onset period. A participant with multiple adverse events within a body system and treatment period is only counted once towards the total of this body system and treatment.

The number and percentage of participants with adverse events by maximum severity or severity of adverse events may be tabulated by body system and preferred term with a breakdown by treatment, if deemed necessary.

The number and percentage of participants with serious adverse events may be tabulated by body system and preferred term with a breakdown by treatment, if deemed necessary.

The number and percentage of participants with adverse events classified as related to study drug will be tabulated by body system and preferred term with a breakdown by treatment.

Seizure related adverse events (based on SOC and/or PT) will be listed and summarized separately as AEs of special interest. The number and percentage of participants with such adverse events will be tabulated by body system and preferred term with a breakdown by treatment.

Only adverse events that will occur at or after first drug intake (i.e., treatment emergent AEs) will be included in the AE summaries.

For the legal requirements of ClinicalTrials.gov and EudraCT, two required tables on treatment emergent adverse events which are not serious adverse events with an incidence greater than 5% and on treatment emergent serious adverse events and SAE suspected to be related to study treatment will be provided by system organ class and preferred term on the safety set population.

If for a same patient, several consecutive AEs (irrespective of study treatment causality, seriousness and severity) occurred with the same SOC and PT:

- a single occurrence will be counted if there is ≤ 1 day gap between the end date of the preceding AE and the start date of the consecutive AE
- more than one occurrence will be counted if there is > 1 day gap between the end date of the preceding AE and the start date of the consecutive AE.

For occurrence, the presence of at least one SAE / SAE suspected to be related to study treatment / non-SAE has to be checked in a block e.g., among AEs in $a \le 1$ day gap block, if at least one SAE is occurring, then one occurrence is calculated for that SAE.

The number of deaths resulting from SAEs suspected to be related to study treatment and SAEs irrespective of study treatment relationship will be provided by SOC and PT.

Other safety evaluations

Not applicable

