#### 8.4.1 Laboratory evaluations

All safety laboratory evaluations will be evaluated locally.

In the case where a laboratory range is not specified by the protocol, but a value is outside the reference range for the laboratory at screening, a decision regarding whether the result is of clinical significance or not shall be made by the Investigator (in consultation with the sponsor as needed) and shall be based, in part, upon the nature and degree of the observed abnormality. If needed, the assessment may be repeated once prior to randomization.

In all cases, the Investigator must document in the source documents, the clinical considerations (i.e., result was/was not clinically significant and/or medically relevant) in allowing or disallowing the participant to continue in the study.

As per [Section 4.6](#), during a Public Health emergency as declared by Local or Regional authorities, i.e., pandemic, epidemic or natural disaster, that limits or prevents on-site study visits, if participants cannot visit the site for protocol-specified safety lab assessments, an alternative local lab collection site may be used.

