## **9 Study discontinuation and completion**

### **9.1 Discontinuation and completion**

#### **9.1.1 Study treatment discontinuation and study discontinuation**

The Investigator must discontinue study treatment for a given participant if, he/she believes that continuation would negatively impact the participant's well-being.

Study drug administration must be discontinued under the following circumstances:

- Participant withdraws consent
- Development of new complete bundle branch block (QRS duration >120ms) for a participant with a normal QRS duration at baseline as determined by the Investigator's interpretation of the ECG findings or an increase in QRS duration that in the opinion of the Investigator may be a risk to participant safety
- QTcF >500 ms for those individuals with a normal QTcF at baseline as determined by the Investigator's interpretation of the ECG findings, or an increase in QTcF that in the opinion of the Investigator may be a risk to participant safety
- A change in atrioventricular conduction that in the opinion of the Investigator may be a risk to participant safety
- An increase in the resting heart rate to >130 beats per minute sustained for >2 minutes as determined by the Investigator, unless there is an obvious alternative explanation other than administration of study drug
- Hypotension, defined as >20 mmHg systolic blood pressure drop (repeat measurement) that is (a) symptomatic or (b) sustained to the point requiring medical intervention
- Any moderate or higher CNS-related AE that in the opinion of the Investigator is suspected to be related to the study drug
- A seizure
- A severe or serious adverse event
- Hypersensitivity reactions and/or injection site reactions of moderate severity or greater

If discontinuation of study drug administration occurs, the investigator should make a reasonable effort to understand the primary reason for the participant's premature discontinuation of study drug administration and record this information.

Participants who discontinue study drug administration or who decide they do not wish to participate in the study further should NOT be considered withdrawn from the study UNLESS they withdraw their consent (see 'Withdrawal of Informed Consent' [Section 9.2](#)).

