## 10.2 Additional Safety Monitoring

### 10.2.1 Liver safety monitoring

To ensure participant safety and enhance reliability in determining the hepatotoxic potential of an investigational drug, a standardized process for identification, monitoring and evaluation of liver events has to be followed.

Please refer to [Table 16-1](#) in [Appendix 1](#) for complete definitions of liver laboratory triggers.

Once a participant is exposed to study treatment, every liver event defined in [Table 16-1](#) should be followed up by the Investigator or designated personnel at the trial site, as summarized below. Additional details on actions required in case of liver events are outlined in [Table 16-2](#) and [Table 16-3](#). Repeat liver chemistry tests (i.e. ALT, AST, TBL, PT/INR, ALP and G-GT) to confirm elevation.

- These liver chemistry repeats should be performed using the local laboratory used by the site. Repeated laboratory test results must be reported as appropriate.
- If the initial elevation is confirmed, close observation of the participant will be initiated, including consideration of treatment interruption if deemed appropriate.
- Hospitalization of the participant if appropriate
- Causality assessment of the liver event
- Thorough follow-up of the liver event should include
  - These investigations can include based on investigator's discretion: serology tests, imaging and pathology assessments, hepatologist's consultancy; obtaining more detailed history of symptoms and prior or concurrent diseases, history of concomitant drug use, exclusion of underlying liver disease

All follow-up information and procedures performed must be recorded as appropriate in the CRF.

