### 10.2.2 Renal safety monitoring

Once a participant is exposed to study treatment, the following two categories of abnormal renal laboratory alert values should be assessed during the study period:

- Serum creatinine increase  $\geq 25\%$  compared to baseline during normal hydration status
- Any one of the following:
  - Urine protein-creatinine ratio (PCR)  $\geq 1\text{g/g}$  or  $\geq 100\text{ mg/mmol}$ , OR
  - New onset dipstick proteinuria  $\geq 3+$ , OR
  - New onset dipstick hematuria  $\geq 3+$  (after excluding menstruation, UTI, extreme exercise, or trauma)

Abnormal renal event findings must be confirmed within 24-48 hours after the first assessment

Once a participant is exposed to study treatment, renal laboratory alerts or renal safety events should be monitored and followed up by the Investigator or designated trial staff as summarized in [Table 16-4](#) in [Appendix 2](#).

Every renal laboratory trigger or renal event as defined in [Table 16-4](#) in [Appendix 2](#) should be followed up by the Investigator or designated personnel at the trial site as summarized in [Table 16-5](#) in [Appendix 2](#).

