## 16 Appendices

### 16.1 Appendix 1: Liver event and laboratory trigger definitions & follow-up requirements

**Table 16-1 Liver event and laboratory trigger definitions**

	Definition/ threshold
Liver laboratory triggers	
 
ALT or AST > 5 × ULN
 

If ALT, AST and total bilirubin normal at baseline:	
 
ALP > 2 × ULN (in the absence of known bone pathology)
 
Total bilirubin > 3 × ULN (in the absence of known Gilbert syndrome)
 
ALT or AST > 3 × ULN and INR > 1.5
 
Potential Hy's Law cases (defined as ALT or AST > 3 × ULN and Total bilirubin > 2 × ULN [mainly conjugated fraction] without notable increase in ALP to > 2 × ULN)
 
Any clinical event of jaundice (or equivalent term)
 
ALT or AST > 3 × ULN accompanied by (general) malaise, fatigue, abdominal pain, nausea, or vomiting, or rash with eosinophilia
 
Any adverse event potentially indicative of a liver toxicity*
 

If ALT or AST abnormal at baseline:	
 
ALT or AST > 2x baseline or > 300 U/L (whichever occurs first)
 

\*These events cover the following: hepatic failure, fibrosis and cirrhosis, and other liver damage-related conditions; non-infectious hepatitis; benign, malignant and unspecified liver neoplasms ULN: upper limit of normal

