## 16.2 Appendix 2: Specific Renal Alert Criteria and Actions and Event Follow-up

**Table 16-4 Specific Renal Alert Criteria and Actions**

Renal Event	Actions
Confirmed serum creatinine increase 25-49%	
 
Consider causes and possible interventions
 
Follow up within 2-5 days
 

Serum creatinine increase $\geq 50\%$	
 
Consider causes and possible interventions
 
Repeat assessment within 24-48 h if possible
 
Consider drug interruption or discontinuation unless other causes are diagnosed and corrected
 
Consider patient hospitalization and specialized treatment
 

New onset dipstick proteinuria $\geq 3+$ OR Protein-creatinine ratio (PCR) $\geq 1\text{g/g Cr}$ (or mg/mmol equivalent as converted by the measuring laboratory)	
 
Consider causes and possible interventions
 
Assess serum albumin & serum total protein
 
Repeat assessment to confirm
 
Consider drug interruption or discontinuation unless other causes are diagnosed and corrected
 

New onset hematuria $\geq 3+$ on urine dipstick	
Assess & document:
 
 
Repeat assessment to confirm
 
Distinguish hemoglobinuria from hematuria
 
Urine sediment microscopy
 
Assess sCr
 
Exclude infection, trauma, bleeding from the distal urinary tract/bladder, menstruation
 
Consider bleeding disorder
 

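### SAP 7.2 counts participants over a limit only for QT/QTcF; the protocol's limits for systolic fall, QRS, liver tests and creatinine get no visible count by arm, and its laboratory shift tables are not carried over

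*SAP*

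**What the plan says.** The protocol judges several harms participant by participant, against a limit or the participant's own baseline:

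- Blood pressure (Protocol 9.1.1): "Hypotension, defined as >20 mmHg systolic blood pressure drop (repeat measurement". The rule goes on to require that the fall cause symptoms or last long enough to need treatment.
- QRS (Protocol 9.1.1): "Development of new complete bundle branch block (QRS duration >120ms", for a participant whose QRS was normal at baseline.
- Liver (Protocol Table 16-1): "ALT or AST > 5 × ULN", with further criteria for ALP, bilirubin, and ALT or AST above 3 x ULN combined with INR, bilirubin or symptoms.
- Kidney (Protocol Table 16-4): "Confirmed serum creatinine increase 25-49" per cent, and a separate row for 50% or more.

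SAP 7.2 plans a count of participants meeting predefined limits for QT/QTcF only. For vital signs, where ranges exist, "abnormalities (and relevant orthostatic changes) will be flagged. Summary statistics will be provided by treatment, cohort and visit/time". QRS gets summary statistics, a split by complete bundle branch block and flagged listings. Laboratory data get summary statistics, flagged listings, and a further listing of all parameters for anyone with an abnormal value.

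Protocol 12.5.1 also plans low/normal/high laboratory shift tables from baseline to the worst on-treatment value. It mentions change-from-baseline summaries where appropriate. The visible SAP 7.2 has no shift tables. Protocol 8.4.1 adds that "All safety laboratory evaluations will be evaluated locally".

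**The concern.** The limits and the summaries are on different scales. The protocol asks whether an individual fell by more than 20 mmHg, exceeded a multiple of ULN, or rose by a given percentage. The visible arm-level tables, apart from QT/QTcF, show averages at each time point. In a cohort of about 29, harm is likely to appear in one or two people, and a reader comparing arms needs to know how many crossed each limit.

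The point matters most for the liver and kidney. Protocol 10.2.1 sets up its liver monitoring to "enhance reliability in determining the hepatotoxic potential of an investigational drug", and Protocol 10.2.2 names "Serum creatinine increase" relative to baseline as an alert. Without counts at those limits, the report's tables cannot summarise what the monitoring was built to detect. A reader would have to assemble it from listings and from the adverse-event tables. A laboratory abnormality enters the adverse-event tables only if it causes symptoms, is judged clinically significant or needs therapy (Protocol 10.1.1).

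**Working it through.** The plan states no figure on this point, so there is none to reproduce. The check compares limits with summaries, then tests how far a mean can stand in for a count.

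**1. Shift tables, if restored.** A low/normal/high class puts 3 x ULN and 5 x ULN in the same cell (high). A creatinine rise stays inside the normal range whenever baseline x (1 + rise) does not exceed ULN:

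- 25% rise: baseline up to ULN/1.25 = 0.80 x ULN.
- 50% rise: baseline up to ULN/1.50 = 0.67 x ULN.

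Such participants would be shown as normal to normal.

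**2. Vital-signs flag.** Protocol Table 8-1 and section 8.4 schedule no standing reading, and participants rest supine or semi-recumbent for the first two hours (Protocol 3). An orthostatic change therefore cannot be derived from scheduled data. The flagging ranges are not given. If the eligibility range of 100 to 160 mmHg (Protocol 5.1) were used, a fall from 150 to 115 is 150 - 115 = 35 mmHg, with neither value flagged.

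**3. Local ranges.** Neither document mentions scaling to ULN, so pooling of raw local values is an inference. With ULNs assumed at 35 and 55 U/L, the same ALT of 110 U/L is 110/35 = 3.14 x ULN at one laboratory and 110/55 = 2.00 x ULN at the other, on either side of 3 x ULN.

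**4. Dilution in the arm mean.** Shift = k x individual change / n, compared with SE = SD/√n, for k affected participants. The documents give about 20 on HSY244; 5:1 applied to 29 gives 29 x 5/6 = 24.2, so both 20 and 24 are used. They give no SDs. Assumed: systolic SD 10 to 20 mmHg, QRS SD 10 to 20 ms, creatinine CV 15 to 25%, ALT SD 0.2 to 0.4 x ULN. The 30 ms QRS rise is also assumed.

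| Change in each affected participant | n = 20, one case | n = 20, two cases | n = 24, one case |
|---|---|---|---|
| Systolic -21 mmHg | 1.05 mmHg (0.23-0.47 SE) | 2.10 (0.47-0.94 SE) | 0.88 (0.21-0.43 SE) |
| QRS +30 ms | 1.5 ms (0.34-0.67 SE) | 3.0 (0.67-1.34 SE) | 1.25 (0.31-0.61 SE) |
| Creatinine +50% | 2.5% (0.45-0.75 SE) | 5.0% (0.89-1.49 SE) | 2.08% (0.41-0.68 SE) |

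Worked case: 21/20 = 1.05; SE = 10/√20 = 2.24 to 20/√20 = 4.47; 1.05/4.47 = 0.23 and 1.05/2.24 = 0.47.

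**5. ALT behaves differently.** With the others at 0.6 x ULN and one participant at 5.01 x ULN, the mean is (19 x 0.6 + 5.01)/20 = 0.82 x ULN, a rise of 37%. The shift is 4.41/20 = 0.22 x ULN, or 2.5 to 4.9 SE. At 3.01 x ULN it is 2.41/20 = 0.12 x ULN, or about 1.3 to 2.7 SE. For n = 24 the ranges are 2.25 to 4.5 and 1.2 to 2.5 SE.

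**6. What a count would show.** One case is 1/20 = 5.0% (1/24 = 4.2%); two are 2/20 = 10.0% (2/24 = 8.3%).

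**The case against.** A reader might infer that these harms vanish. They do not. Vital signs, ECG and laboratory data are listed by participant with abnormalities flagged, anyone with an abnormal laboratory value gets a separate full listing, and qualifying findings reach the adverse-event tables. Table 8-1 schedules only one post-dose chemistry sample, at end of study. With about 29 participants, one or two flagged cases are easy to find. If the summary statistics include minimum and maximum, an extreme raw value would also show in the table. All of this stands. It leaves unflagged changes within range, and the missing count by arm.

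A reader might also infer that laboratory data are summarised only on the raw scale. Protocol 12.5.1 contradicts that. Its shift tables, read against each laboratory's own range, do not depend on units. The narrower point is that the visible SAP does not carry them over, and that they are too coarse for the protocol's limits.

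Three further cautions stand:

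- A systolic fall above 20 mmHg is not in itself the protocol's hypotension rule, which also requires symptoms or intervention.
- Redacted text follows the ECG summary in SAP 7.2, and MMRM and concentration-effect analyses may be applied to ECG parameters. It cannot be said that no QRS count exists, only that none is visible.
- INR is not in the scheduled panel of Protocol 8.4.1, so INR-based liver criteria cannot be counted for everyone.

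**Conclusion.** The point holds as a cheap improvement to reporting. The visible SAP extends a count at limits to QT/QTcF and to none of the other four measures, and omits the protocol's laboratory shift tables. Range flags and low/normal/high classes cannot separate 3 x from 5 x ULN, show a 25 to 50% creatinine rise within the normal range, or flag a within-range systolic fall from pre-dose.

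Under the assumed spreads, one affected participant moves the HSY244 mean by less than one standard error for blood pressure, QRS and creatinine. Two cases reach at most about 1.5 standard errors. The dilution argument does not extend to a marked ALT rise; for liver tests the case rests on the missing counts and the likely mixing of local ranges. The documents do not support saying that the plan would miss such harm. They support saying that its arm-level tables do not show how many participants crossed each limit.

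**What to change.** In SAP 7.2:

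1. Restore the laboratory shift tables of Protocol 12.5.1, classifying each value by the range of the laboratory that produced it.
2. Add one table by arm counting participants at the protocol's existing numerical limits:
   - systolic fall above 20 mmHg from pre-dose, labelled as only the numerical component of the hypotension rule in Protocol 9.1.1, with its time window stated because the 180-minute reading can follow electrical cardioversion under sedation;
   - new QRS above 120 ms, unless the redacted text already covers it;
   - the laboratory-based criteria of Table 16-1, with those using INR counted only where INR was measured and that denominator shown;
   - creatinine increase of 25 to 49% and of 50% or more, marking which were confirmed on repeat.
3. Summarise liver tests as multiples of the local ULN and creatinine as percentage change from pre-dose.
4. Remove the reference to orthostatic changes, or state which readings it would use.

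The cost is SAP wording and minor programming, provided local reference ranges are held with the results, as flagging already requires. No new data collection and no new clinical rule are needed.

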### **12.5 Analysis of secondary endpoints/estimands**

#### **12.5.1 Safety endpoints**

For all safety analyses, the safety set will be used. All listings and tables will be presented by treatment group and cohort.

Safety summaries (tables, figures) include only data from the on-treatment period with the exception of baseline data, which will also be summarized where appropriate (e.g., change from baseline summaries). In particular, tables for adverse events (AEs) will summarize only on-treatment events, with a start date during the on-treatment period (treatment-emergent AEs). The on-treatment period lasts from the date of administration of study treatment to EOS visit.

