#### **Adverse events**

All information obtained on adverse events will be displayed by treatment group, cohort and participant.

The number (and percentage) of participants with treatment emergent adverse events (events started after the first dose of study medication or events present prior to start of double-blind

treatment but increased in severity based on preferred term) will be summarized in the following ways:

- by treatment, primary system organ class and preferred term.
- by treatment, primary system organ class, preferred term and maximum severity.
- by treatment, Standardized MedDRA Query (SMQ) and preferred term.

A participant with multiple adverse events within a primary system organ class is only counted once towards the total of the primary system organ class.

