### **Clinical laboratory evaluations**

All laboratory data will be listed by treatment group, cohort, participant, and visit/time and if normal ranges are available abnormalities will be flagged. Summary statistics will be provided by treatment, cohort and visit/time. Shift tables using the low/normal/high/ (low and high) classification will be used to compare baseline to the worst on-treatment value.

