1.4 Study design and treatment

This is a randomized, placebo-controlled, investigator- and participant-blinded study to evaluate the efficacy, safety, tolerability, and pharmacokinetics of HSY244 in participants with AF. An initial cohort (Cohort 1) of approximately 29 participants (approximately 20 participants receiving HSY244) is planned to be enrolled to evaluate a single 150 mg i.v. dose of HSY244 for AF cardioversion to sinus rhythm.

Commercially Confidential Information

Participants with AF that meet clinical criteria for direct current cardioversion will be screened, and on Day 1, after eligibility is confirmed, administration of a 15 minute i.v. infusion of HSY244 or placebo will occur. Participants will then be monitored for cardioversion to sinus rhythm. For those remaining in AF after 90 minutes, direct current cardioversion can be performed. Participants will be monitored for at least 3 hours, although overnight observation will be available. Participants will be evaluated for safety and pharmacokinetic assessments during end of study assessments, which are to occur on Day 5 (96 hours post dose) \pm 24 hours.

2 First interpretable results (FIR)

First interpretable results (FIR) will be provided for this trial. Commercially Confidential Information

The FIR will focus on the following analyses:

- 1. Participant Disposition
- 2. Demographics and baseline characteristics by cohort. Baseline characteristics include, but not limited to: age, sex, race, ethnicity, BMI, relevant medical history/current medical conditions (previous diagnosis of heart failure, etc.), duration of current AF episode, etc.
- 3. Safety Results
 - a. Number and percentage of adverse events by body system and Cohort
 - b. Number and percentage of adverse events by preferred term and Cohort
- 4. Pharmacokinetic results for each Cohort
- 5. Pharmacodynamic analyses include, but are not limited to:
 - a. Fisher's exact test comparing conversion rates between HSY244 and placebo
 - b. MMRM analysis of ECG and heart rate parameters comparing HSY244 and placebo
 - c. Concentration effect analysis of QT and Heart Rate parameters
 - d. Time to event analysis for the time to conversion and time in sinus rhythm after conversion comparing HSY244 and placebo
 - e. AF burden comparison between HSY244 and placebo

3 Interim analyses

4 Statistical methods: Analysis sets

For all analysis sets, participants will be analyzed according to the study treatment(s) received.

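### SAP 7.2 makes the severity table optional and omits the SMQ and laboratory shift tables that Protocol 12.5.1 commits to; SAP section 2 words the first-results AE tables without treatment arm

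*SAP*

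**What the plan says.** Protocol 12.5.1 states its safety outputs as commitments. Besides the table by system organ class (SOC) and preferred term (PT), treatment-emergent AEs are to be summarised "by treatment, primary system organ class, preferred term and maximum severity" and "by treatment, Standardized MedDRA Query (SMQ) and preferred term". For laboratory data, "Shift tables using the low/normal/high/ (low and high) classification will be used to compare baseline to the worst on-treatment value". A general display rule opens the section: "All listings and tables will be presented by treatment group and cohort".

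SAP 1.1 describes the SAP as implementing the protocol's planned analysis. On the same outputs, SAP 7.2 says that counts and percentages of participants with AEs "by maximum severity or severity of adverse events may be tabulated by body system and preferred term with a breakdown by treatment, if deemed necessary". Its AE text has no SMQ table. Its laboratory text provides listings, flags for abnormal values, a separate listing for participants with any abnormal value, and summary statistics, but no shift table. The seizure group is worded loosely: "Seizure related adverse events (based on SOC and/or PT) will be listed and summarized separately as AEs of special interest".

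SAP section 2 lists the first interpretable results. Item 3a is "Number and percentage of adverse events by body system and Cohort", and item 3b is the same by preferred term. Neither names an arm, whereas several pharmacodynamic items in the same list, including the Fisher test of conversion rates, compare HSY244 with placebo.

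**The concern.** A SAP that implements a protocol may add detail, but it should not turn a planned output into an optional one, or leave it out, without saying why. Three features of this trial make the point more than editorial.

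- **Severity is used in the trial's own rules.** The stopping rules in Protocol 9.2.2 and the discontinuation rules in Protocol 9.1.1 both refer to moderate or worse events. Protocol 6.4 lets the statistician open the randomization list at interim analyses and share unblinded data with the clinical team. The choice to produce a severity table could therefore be made by people who have seen results by arm.
- **SMQs are the protocol's only planned grouping across preferred terms.** Protocol 4.5.1 flags central nervous system effects as a risk. The seizure group, the nearest substitute in the SAP, is not fixed: a SOC rule and a PT rule can select different events.
- **Laboratory values come from local laboratories** ("All safety laboratory evaluations will be evaluated locally"). A low/normal/high shift can judge each value against its own laboratory's range. Summary statistics of raw values do not.

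For the first results, an AE table without arm gives the sponsor's earliest readers no placebo comparison.

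**Working it through.** **Step 1: set the texts side by side.**

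| Output | Protocol 12.5.1 | SAP |
|---|---|---|
| AEs by SOC and PT, by treatment | firm | firm (7.2) |
| AEs by maximum severity | firm | optional (7.2) |
| AEs by SMQ and PT | firm | absent from visible text |
| Laboratory shift, baseline to worst value on treatment | firm | absent from visible text |
| Arm shown in safety tables | arm and cohort | first results: cohort only (section 2); AE tables in 7.2: by treatment |
| Reason for the change | – | none stated |

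**Step 2: could redaction explain the gaps?** In SAP 7.2 the redacted block sits in the ECG text. The visible AE and laboratory paragraphs read continuously, so redaction is an unlikely explanation there. In SAP section 2 a redaction follows the opening sentence, so an arm breakdown stated at that point cannot be excluded.

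**Step 3: arm sizes for the first-results tables.** Inputs from Protocol section 3: about 29 randomised in Cohort 1, about 20 of them on HSY244, allocation 5:1.

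- From the total and the ratio: 29 × 5/6 = 24.2, so 24 and 5.
- From the total and the HSY244 count: 29 − 20 = 9, so 20 and 9.
- From the HSY244 count and the ratio: 20 × 6/5 = 24 in all, so 20 and 4.

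The stated figures do not give a single split. They are approximate and the sample-size text is redacted, so I use the splits as a range of assumptions and do not call this an error here.

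**Step 4: effect of pooling the arms.** Suppose *x* participants have an event, all on HSY244 (an assumption). By arm the rate is *x*/n_A; pooled it is *x*/(n_A + n_P). The ratio is n_A/(n_A + n_P), whatever *x* is.

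| HSY244 / placebo | Ratio | *x* = 4, by arm | *x* = 4, pooled |
|---|---|---|---|
| 20 / 9 | 20/29 = 0.69 | 4/20 = 20.0% vs 0% | 4/29 = 13.8% |
| 24 / 5 | 24/29 = 0.83 | 4/24 = 16.7% vs 0% | 4/29 = 13.8% |
| 20 / 4 | 20/24 = 0.83 | 4/20 = 20.0% vs 0% | 4/24 = 16.7% |

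The HSY244 rate falls by 17% to 31% of its value. If placebo also has events, the fall is smaller. With rates of 20% and 5%, the pooled rate is (20 × 0.20 + 9 × 0.05)/29 = 15.3%, or (24 × 0.20 + 5 × 0.05)/29 = 17.4%. In every case the table shows one figure and no contrast. The calculation counts participants; items 3a and 3b are worded as counts of events, for which the documents give no denominator.

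**The case against.** The best case against this point is that little is lost in the final report. Most of it stands, and it limits the point.

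- **A reader might infer that a nervous-system or liver signal would be hidden in the final report.** The documents do not support that. The main AE table, the related-AE table and the seizure table in SAP 7.2 are all firm and by treatment, and the main table counts each participant once per body system, so related terms in one body system share a total. Whether the effects of concern would fall in different body systems depends on MedDRA coding that the documents do not give.
- **A reader might infer that laboratory safety rests on raw means alone.** It does not. Abnormal values are flagged, and participants with any abnormal value get a separate full listing. Chemistry is scheduled only once after dosing, at the end-of-study visit (Protocol Table 8-1), so for that panel a shift table mainly organises what the listings already show.
- **A reader might infer that serious AEs (SAEs) are left optional.** One sentence in SAP 7.2 is conditional, but a later paragraph commits to SAE tables by SOC and PT for the registries. Protocol 12.5.1 lists no SAE table, so there is no commitment to restore.
- **On the first results,** naming cohort does not forbid showing arm, the protocol's display rule still applies, and the redacted line may settle it. This is fair, which is why the point is put as a wording gap.
- **The SAP nowhere revokes the SMQ and shift tables,** and SAP 1.1 mentions further analysis-plan documents that are not in view. They may carry the missing tables, but the SAP is where the protocol's analyses are to be implemented, and it neither lists these tables nor points to them.

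None of this makes the severity table firm or supplies the other two outputs.

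**Conclusion.** The concern holds as a mismatch between the two documents. One output promised in Protocol 12.5.1 has become discretionary in SAP 7.2, and two are missing from its visible text, all without a stated reason. This rests on reading the texts and on no numerical assumption.

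The first-results part is conditional. If items 3a and 3b are produced as worded and the redacted line adds no arm, the placebo comparison is lost, and an event rate confined to HSY244 is scaled by about 0.69 to 0.83. Those factors assume 20/9 and 24/5 splits and no placebo events. The missing contrast matters more than the scaling, and it does not reach the AE tables of SAP 7.2.

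The point does not touch the primary analysis. It is worth correcting because safety is a secondary objective and the correction is cheap.

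**What to change.** In SAP 7.2:

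1. Make the AE table by maximum severity unconditional, by treatment.
2. Add the AE table by SMQ and PT, by treatment.
3. Add the low/normal/high laboratory shift table, keeping the protocol's comparison of baseline with the worst value on treatment.
4. Define the seizure group by one fixed rule, either an SMQ or a PT list.

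If the sponsor prefers not to produce item 1, 2 or 3, record the change from the protocol and its reason before unblinding.

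In SAP section 2, item 3, tabulate participants with AEs, by treatment within cohort.

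The cost is a SAP wording change and a few standard tables from data already collected. Neither document calls for a special grouped nervous-system line or liver tests tabulated as multiples of the upper limit of normal, and neither is needed to close this gap.
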